4.5.2 Measurements of Treatment Compliance

4.5.2.1 Study Treatment Compliance

Compliance to the study treatment regimen will be based on the drug accountability records. Compliance will be determined as the percentage of expected capsules that a subject should have taken based on their dosing days on study relative to the drug accountability reporting of their actual number of capsules taken. The following definitions are applied:

- **Expected Number of Dosing Days:** the last dose date reported on the End of Treatment eCRF minus the onsite first study administration that takes place at Visit 2 (Day 1) + 1.
- **Expected Number of Capsules to be Taken:** Expected Number of Dosing Days multiplied by two (standard dosing includes two capsules per day).
- **Actual Number of Capsules Taken:** The summation of all entries of “Dispensed Amount (Capsules)” reported on the “Drug Accountability – Dispensed” eCRF minus the summation of all entries of “Amount Returned (Capsules)” reported on the “Drug Accountability – Returned” eCRF. Any capsules reported as lost will be further subtracted from this total. Subjects that are missing their return records are assumed to have taken all dispensed capsules for the missing bottle.

Treatment compliance (%) is defined as the Actual Number of Capsules Taken divided by the Expected Number of Capsules to be Taken, multiplied by 100.

Dosing compliance will be summarized using descriptive statistics, by treatment group and overall subjects combined, for the Safety Analysis Set. The number and percentage of subjects who are < 80% compliant and ≥ 80% compliant within each treatment group and overall subjects combined will be summarized.

4.5.2.2 Emollient Use

Subject exposure to on-study background therapy emollient-use will be summarized by treatment group and overall subjects combined for the Safety Analysis Set. The number and percentage of subject’s reporting use of a non-study permitted emollient at any time on study will be summarized based on self-reporting of emollient use by the daily diary. Summarization of concomitant emollient based on the medication reported will also be provided as described in [Section 4.5.6.4](#).

4.5.3 Adverse Events

A TEAE is defined as those AEs with onset after the first dose of study drug or existing events that worsened after the first dose during the study. Treatment-emergent AEs will be summarized by treatment group and overall subjects combined. Events reported with a partial onset date (e.g., month and year are reported but the day is missing) will be considered to be treatment-emergent if it cannot be confirmed that the event onset was prior to the first dose of study drug based on the available date entries.

Verbatim terms on case report forms will be mapped to preferred terms and system organ classes using MedDRA, version 26.0.

Summaries that are displayed by system organ class and preferred terms will be ordered by descending incidence of system organ class and preferred term within each system organ class. Summaries displayed by preferred term only will be ordered by descending incidence of preferred term. Summaries of the following types will be presented:

- Overall summary of number of unique TEAEs and treatment-emergent SAEs and subject incidence of TEAEs meeting various criteria;
- Subject incidence of TEAEs by MedDRA system organ class and preferred term;
- Subject incidence of the most frequently-occurring TEAEs (i.e., TEAEs occurring in $\geq 10\%$ of the Safety Analysis Set) by MedDRA preferred term;
- Subject incidence of TEAEs by CTCAE grade, MedDRA system organ class, and preferred term;
- Subject incidence of TEAEs by relationship to study drug, MedDRA system organ class, and preferred term;
- Subject incidence of the most frequently-occurring TEAEs related to study drug (i.e., related TEAEs occurring in $\geq 10\%$ of the Safety Analysis Set) by MedDRA preferred term;
- Subject incidence of CTCAE grade 3 or higher TEAEs related to study drug by MedDRA system organ class and preferred term; and
- Subject incidence of SAEs by MedDRA system organ class and preferred term.

At each level of summarization (e.g., any AE, system organ class, and preferred term), subjects experiencing more than one TEAE will be counted only once. In the summary of TEAEs by CTCAE grade, subjects will be counted once at the highest grade reported at each level of summarization; in the summary of TEAEs by relationship, subjects will be counted once at the closest relationship to study drug. Related events include those reported as “Related” to study treatment; events considered not related are those reported as “Not Related” to study treatment.

Adverse event data will be presented in data listings by subject, treatment group, and event. Serious AEs and AEs leading to discontinuation of the study drug will be presented in separate data listings.

4.5.4 Deaths, Other Serious Adverse Events, and Other Significant Adverse Events

All deaths during the study, including the post treatment follow-up period, will be listed by subject, to include any corresponding details associated with death. Serious AEs and other significant AEs, including those that led to discontinuation or interruption of the study drug, will be provided in separate subject data listings.

4.5.5 Clinical Laboratory Evaluation

All descriptive summaries of laboratory results will be based on data analyzed by the central laboratory and presented in conventional units. All data will be included in by-subject data listings. Laboratory measurements identified as abnormal (i.e., outside the normal range) will also be listed separately by subject, laboratory test, and unit. In addition, normal ranges provided by the central laboratory will be presented in a separate listing.

Clinical laboratory measurements, including serum chemistry, hematology, and coagulation will be summarized by treatment group and overall subjects combined. Descriptive statistics will be presented for observed values and changes from baseline at each visit where parameters were scheduled to be collected per the clinical study protocol.

Where applicable, laboratory results will be classified as “low,” “normal,” or “high” with respect to the parameter-specific reference ranges (i.e., below the lower limit of the normal range, within the normal range, or above the upper limit of the normal range). Three-by-three contingency tables will be presented for each laboratory parameter to summarize the shift from the baseline category to the worst post-baseline measurement, defined as the value numerically farthest outside of the normal range across all post-baseline visits through the end of the study. Summary results will include the count and percentage of subjects within each shift category and treatment group and overall subjects combined.

The clinical study protocol includes guidance associated with the monitoring and interruption of study drug for suspected DILI. Subjects with the following post-baseline ALT or AST values will be assessed for the following DILI criteria:

- ALT or AST $>8 \times$ ULN
- ALT or AST $>5 \times$ ULN for more than 2 weeks: subjects must have confirmed elevated values by subsequent repeat testing that shows at least two weeks of elevated values.
- ALT or AST $>3 \times$ ULN AND total bilirubin $>2 \times$ ULN OR INR >1.5
- ALT or AST $>3 \times$ ULN with the appearance of new onset fatigue, nausea, vomiting, right upper quadrant pain or tenderness, fever, rash, and/or eosinophilia ($>5\%$).

Subjects qualifying in any of the above treatment-emergent DILI criteria will be presented in a data listing.

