# 15.6. Safety Analysis

The Safety Analysis Set will be used for the summaries of the safety data. Safety data will be summarized by treatment group and overall.

The safety and tolerability of EP262 will be assessed by comparing the frequency, causality, and severity of AEs as well as treatment discontinuations due to AEs. AEs will be coded using the Medical Dictionary for Regulatory Activities (MedDRA) by SOC and Preferred Term. AEs that begin after the first administration of study drug, or existing AEs that worsen after the first dose of study drug, are considered treatment emergent. All AE summaries will include TEAEs, and all AEs will be presented in data listings.

Concomitant medications will be coded using the World Health Organization (WHO) Drug Dictionary and summarized descriptively by Anatomic Therapeutic Chemistry (ATC) class using counts and percentages. Medications started prior to the first dose of study drug will be indicated in the data listings. Use of protocol-permitted emollient will also be summarized descriptively.

Changes in vital signs, standard 12-lead ECGs, and laboratory evaluations will be summarized descriptively.

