Additional considerations are made for TEAEs falling under certain system organ classes. The study drug must be discontinued for the following TEAEs and CTCAE grades:

- CTCAE Grade 2 or higher in the Cardiac Disorders system organ class
- CTCAE Grade 2 or higher in terms of Bone marrow hypocellular, lymphocyte count decreased, lymphocyte count increased, or myelodysplastic syndrome
- CTCAE Grade 3 or higher in other system organ classes

3.4.4.2 *Laboratory Parameters*

Samples for the following laboratory tests should be collected after an overnight fast (at least 8 hours):

- Chemistry: sodium, albumin, alkaline phosphatase (ALP), bicarbonate, calcium, corrected calcium, chloride, bilirubin (total, indirect, and direct), AST, ALT, blood urea nitrogen, urea, creatinine, glucose, magnesium, phosphorus, potassium, creatine phosphokinase, total cholesterol, triglycerides, high-density lipoprotein cholesterol, low-density lipoprotein cholesterol, lactate dehydrogenase, gamma-glutamyl transferase, and total protein
- Hematology: hemoglobin, hematocrit, mean corpuscular hemoglobin, mean corpuscular hemoglobin concentration, mean corpuscular volume, white blood cell count (total and differential), red blood cell count, platelet count, and platelet volume

- Urinalysis: leukocyte esterase, nitrites, pH, protein, specific gravity, glucose, occult blood, ketones, bilirubin, and urobilinogen; microscopic analysis is to be performed only if protein, leukocyte esterase, blood or nitrite is positive
- Coagulation: activated partial thromboplastin time, international normalized ratio (INR), and prothrombin time
- Pregnancy testing: required for all females; serum test at Screening (Visit 1) and urine test for all other visits where pregnancy testing is required

The urine pregnancy test for female subjects will be conducted locally; all other planned laboratory evaluations of safety will be conducted at a central laboratory. Details for sample collection, processing, storage, and shipment will be provided in the Laboratory Manual.

3.4.4.3 *Other Laboratory Evaluations*

Samples for the following laboratory tests will be collected:

- Serology: HIV I/II, HBV (hepatitis B surface antigen), HCV

These planned laboratory evaluations will be conducted at a central laboratory. See the Laboratory Manual for additional details.

3.4.4.4 *Medical History*

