4.1.2 Summarization by Visit

Data summarized by study visit will be based on the nominal, scheduled visit label as reported on the eCRF.

Whenever possible, subjects should remain in the study and complete the remaining study visits and assessments even when study drug has been discontinued. Subjects who discontinue study drug for any reason and continue with the study visits as planned through Visit 4 (Week 6) (participating only in PD and safety, but not PK measures) will participate in the Follow-Up Visit if the last dose of study drug was administered less than 4 weeks before Visit 4 (Week 6) to ensure that at least 4 weeks of follow-up data are collected for all randomized subjects. Subjects that discontinue treatments early and complete the remaining study visits will be summarized according to their planned treatment group, unless otherwise noted.

If a subject discontinues study drug and chooses not to complete all of the remaining study visits, the subject should have the Early Treatment Termination visit conducted as soon as possible after the last dose of study drug, ideally within 2 days after the last dose of study drug, and a Follow-Up Visit approximately 4 weeks (± 3 days) after the last dose of study drug if at least 4 weeks of follow-up data have not already been collected. The Early Treatment Termination visit will be mapped and summarized with the next treatment scheduled nominal visit, according to the schedule of events, based on the last visit completed per protocol if the Early Treatment Termination visit falls within the study day visit window defined for that nominal visit.

Data collected at unscheduled visits will not be included in by-visit summaries, but will be considered when endpoint derivations potentially include multiple visits (e.g., determination of baseline value, determination of worst post-baseline value, etc.). All data will be included in subject listings.

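### The laboratory shift table keeps one 'worst' value per subject and parameter, so a subject with both a low and a high value is counted in one direction only

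*SAP*

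**What the plan says.** SAP 4.5.5 (Clinical Laboratory Evaluation) sets out the categorical display in three steps.

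- Categories: "laboratory results will be classified as “low,” “normal,” or “high” with respect to the parameter-specific reference ranges".
- Display: "Three-by-three contingency tables will be presented for each laboratory parameter to summarize the shift from the baseline category to the worst post-baseline measurement".
- Choice of the worst measurement: "defined as the value numerically farthest outside of the normal range across all post-baseline visits through the end of the study".

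The section gives no separate worst-low and worst-high, and no direction of concern for any parameter.

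It also provides other laboratory outputs: descriptive statistics by visit for observed values and changes from baseline, a listing of all data, and a listing of abnormal values: "Laboratory measurements identified as abnormal (i.e., outside the normal range) will also be listed separately by subject, laboratory test, and unit". SAP 4.1.1 includes the minimum and maximum in summaries of continuous variables. For unscheduled samples, SAP 4.1.2 states: "Data collected at unscheduled visits will not be included in by-visit summaries, but will be considered when endpoint derivations potentially include multiple visits". Its examples of such derivations include the worst post-baseline value.

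The protocol's own commitment in 15.6 is general: "Changes in vital signs, standard 12-lead ECGs, and laboratory evaluations will be summarized descriptively".

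**The concern.** Change from baseline in clinical laboratory parameters is one of the primary endpoints (Protocol section 6), and the plan makes no formal comparison. The safety reading therefore rests on the descriptive displays. Among the laboratory outputs, the shift table is the only one that counts subjects as low, normal or high by arm. The by-visit tables are continuous summaries, and the abnormal-value and liver-injury outputs are listings.

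One worst value that may lie in either direction forces a choice when a subject has both. The choice is made on raw distance from the range, which is not a measure of clinical importance. The documents show that both directions of one parameter can matter: among the mandatory discontinuation terms, SAP 3.4.4.1 names "lymphocyte count decreased, lymphocyte count increased".

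Two features widen the gap. The window runs to the end of the study, so a value from the follow-up visit, about four weeks after the last dose, can displace a value seen on treatment. Unscheduled values compete to be the worst value but are left out of the by-visit summaries. With about 30 subjects randomized 2:1, or roughly 20 and 10 per arm, one subject is 5% or 10% of an arm.

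**Working it through.** The plan attaches no figure to this rule, so there is none to reproduce. The check applies the rule directly and then asks how often it matters.

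**Inputs from the documents.** There are three scheduled post-baseline samples for a completer, at Weeks 3, 6 and 10 (Protocol Appendix A), and about 30 subjects (SAP 3.1). The chemistry, hematology and coagulation panels in SAP 3.4.4.2 come to 44 parameters if the white cell differential is taken as five cell types: 27 + 14 + 3.

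**Assumptions.** The documents give no reference limits, tail rates, skewness or within-subject correlation. All values used for these below are assumed.

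**1. The rule on one subject.** Write LLN and ULN for the lower and upper limits of normal. The distance is LLN − x for a low value and x − ULN for a high value; the larger is kept. Assume a range of 1.0 to 4.0.

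- Values 0.4, 2.0, 4.7: distances are 1.0 − 0.4 = 0.6 below and 4.7 − 4.0 = 0.7 above. The subject is counted as high, and the low drops out of the table.
- Values 0.4, 2.0, 4.5: distances are 0.6 below and 0.5 above. The subject is counted as low, and the high drops out.

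Masking therefore works both ways.

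**2. Is there a lean?** A non-negative analyte cannot lie further below the range than LLN. Any value above ULN + LLN (5.0 here) therefore outranks every possible low. How often this decides the matter depends on the distribution. In a simulation of 4 million subjects with three independent visits and 2.5% in each tail, the share of conflicts in which the high was kept was:

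| Distribution | High kept |
|---|---|
| Symmetric (normal) | 50% |
| Lognormal, log-SD 0.1 | 61% |
| Lognormal, log-SD 0.3 | 79% |
| Lognormal, log-SD 0.5 | 90% |
| Lognormal, log-SD 0.8 | 97% |

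**3. How often does one subject have both?** For k independent visits with probability p in each tail, P(both) = 1 − 2(1 − p)^k + (1 − 2p)^k. With k = 3 and p = 0.025 this is 1 − 2(0.92686) + 0.85738 = 0.00366.

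| p per tail | P(both), 3 visits | Expected among 30 subjects, per parameter |
|---|---|---|
| 1% | 0.06% | 0.02 |
| 2.5% | 0.37% | 0.11 |
| 5% | 1.4% | 0.43 |
| 10% | 5.4% | 1.6 |

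**4. Within-subject correlation.** Repeat values from one person are usually correlated. At 2.5% tails, the simulated rate falls from 0.37% to about 0.04% at a correlation of 0.3, and to about 0.003% at 0.5.

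**5. Over the whole panel.** Take 22 to 44 parameters; the lower figure is half the panel, as an allowance for parameters where only one direction is of interest. That gives 30 × 22 = 660 to 30 × 44 = 1,320 subject-parameter pairs.

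- Independent visits: 660 × 0.00366 = 2.4 to 1,320 × 0.00366 = 4.8 pairs.
- Correlation 0.3: 660 × 0.0004 = 0.3 to 1,320 × 0.0004 = 0.5.
- Correlation 0.5: 660 × 0.00003 = 0.02 to 1,320 × 0.00003 = 0.04.

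These counts include masked highs as well as masked lows. They describe background variation only, and do not model a fall on treatment followed by a rebound after it.

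**The case against.** The strongest reply is that little is really lost. Every value is listed, and every out-of-range value is listed again. A low at a scheduled visit enters its arm's summary for that visit, where the printed minimum would often reveal it. The primary endpoint is change from baseline, which the by-visit tables deliver, and the shift table supplements them. This stands, and it limits the point to one table. It does not cover an unscheduled value outside the adverse event tables, which reaches listings only. Protocol 11.1.1 keeps abnormalities judged not clinically significant from being reported as adverse events.

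A reader might infer that a lymphocyte decrease meeting the discontinuation rule could go uncounted. The documents do not support that. The rule in Protocol 8.5.1 and SAP 3.4.4.1 is defined on treatment-emergent adverse events, so any such decrease is already one. SAP 4.5.3 tabulates these by arm, preferred term and grade, and the decreased and increased terms are separate.

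A reader might also infer that the rule favors highs in general. It does not: distance is treated symmetrically, and the lean appears only for right-skewed, zero-bounded analytes.

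**Conclusion.** The weakness is real but small. As written, SAP 4.5.5 cannot show both directions for one subject and parameter, and the direction it keeps is decided by raw distance. The omission affects the only by-arm low/normal/high laboratory table; the value itself is not lost from the report.

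With three scheduled post-baseline samples and assumed 2.5% tails, about 0.37% of subject-parameter pairs are affected if visits are independent, and about 0.04% at a within-subject correlation of 0.3. It is tempting to read the independent-visit figure as two to five hidden events in the trial. That count depends on independence and falls below one at a correlation of 0.3. It also mixes masked highs with masked lows, so it does not measure undercounted decreases. Wider tails raise the rate, to 5.4% per pair at 10% tails with independent visits.

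The case for change does not rest on any of these rates. The single-value rule discards information that a safety shift table exists to show, and a table without that defect is available at little cost.

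**What to change.** In SAP 4.5.5, replace the single shift table with two per parameter:

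- baseline category to the category of the lowest post-baseline value;
- baseline category to the category of the highest post-baseline value.

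State that each is taken over all post-baseline values, scheduled and unscheduled, and that a subject may count as low in the first and high in the second. The definition of worst by numeric distance is then no longer needed for this display. In the example with values 0.4, 2.0 and 4.7, the subject is counted once as low and once as high.

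The cost is a change of SAP wording and one more table block per parameter. No new data are needed. The change should be made before unblinding.

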4.5.6 Vital Signs, Physical Findings, and Other Observations Related to Safety

4.5.6.1 Vital Signs

Vital sign parameter measurements will be summarized by treatment group and overall subjects combined. Descriptive statistics will be presented for results and change from baseline at each visit where parameters were scheduled to be collected.

Height, body weight and body mass index (BMI) will be summarized by treatment group and overall subjects combined. Body mass index will be calculated as weight (kg) / (height at screening [cm] / 100)². Height at screening, body weight, and BMI will be summarized using descriptive statistics for observed measurements and changes from baseline (body weight only) at each visit where parameters were scheduled to be collected.

4.5.6.2 12-Lead Electrocardiogram

Twelve-Lead ECG interval parameters will be summarized by treatment group and overall subjects combined. Descriptive statistics will be presented for observed values and changes from baseline at each visit where parameters were scheduled to be collected.

Twelve-lead ECG will be classified by the investigator as “normal,” “abnormal, not clinically significant,” or “abnormal, clinically significant.” Three-by-three contingency tables will be presented to summarize the shift from the baseline category to the worst post-baseline value. Summary results will include the count and percentage of subjects within each shift category and treatment group and overall subjects combined.

Prolonged QTc (using corrected QT interval using Fridericia’s formula [QTcF] and QTc interval using Bazett’s formula [QTcB]) intervals will be summarized as QTc measurements (msec) that are >450, >480, and >500 at each visit where ECG is routinely collected per the clinical study protocol. Change from baseline categories will also be summarized for measurements that represent a change >30 or >60 relative to the baseline value. Summary results will include the percentage of subjects within each category and treatment group and for all subjects combined.

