4.1.1 Reporting Conventions

Tables will be summarized by treatment group. All tables, exclusive of PD and pharmacokinetic (PK) analyses, will also include a column for all subjects combined. In general, all data collected and any derived data will be presented in subject data listings, for all enrolled subjects. Listings will be ordered by subject number, treatment

group, and assessment or event date. The treatment group presented in listings will be based on the planned assignment, unless otherwise noted.

In general, continuous variables will be summarized to indicate the study population sample size (N), number of subjects with available data (n), mean, SD, SE, median, first (Q1) and third (Q3) quartiles, minimum, and maximum values. Categorical variables will be summarized by the population size (N), number of subjects with available data (n), number of subjects in each category, and the percentage of subjects in each category. Unless otherwise noted, the denominator to determine the percentage of subjects in each category will be based on the number of subjects with available data. Select ordinal data may be summarized using both descriptive statistics and counts and percentages of subjects in each category, as appropriate.

Non-zero percentages will be rounded to one decimal place. Rounding conventions for presentation of summary statistics will be based on the precision of the variable of summarization, as it is collected in its rawest form (i.e., on the eCRF or as provided within an external file) and are outlined as follows:

- The mean and median will be rounded to one more decimal place than the precision of the variable of summarization;
- Measures of variability (e.g., SD, SE) will be rounded to two more decimal places than the precision of the variable of summarization; and
- Minimum and maximum values will be presented using the same precision as the variable of summarization.

Other statistics (e.g., CIs) will be presented using the same general rules outlined above, or assessed for the most appropriate presentation based on the underlying data.

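### QTc above 450, 480 and 500 msec is counted by scheduled visit only, so an unscheduled outlier enters no absolute-threshold count and the table may not show how many subjects ever exceeded a limit

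*SAP*

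**What the plan says.** SAP 4.5.6.2 (12-Lead Electrocardiogram) plans three displays besides descriptive statistics by visit.

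- **Absolute QTc limits.** QTcF and QTcB are summarised as "QTc measurements (msec) that are >450, >480, and >500 at each visit where ECG is routinely collected per the clinical study protocol". The percentage of subjects per category is reported by treatment group and overall. No row across visits is named.
- **QTc change.** "Change from baseline categories will also be summarized for measurements that represent a change >30 or >60 relative to the baseline value". No visit basis and no worst-value basis is given.
- **Investigator's call** (normal, abnormal not clinically significant, abnormal clinically significant). "Three-by-three contingency tables will be presented to summarize the shift from the baseline category to the worst post-baseline value".

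SAP 4.1.2 sets the general rule. "Data collected at unscheduled visits will not be included in by-visit summaries", but such data "will be considered when endpoint derivations potentially include multiple visits"; determining the worst post-baseline value is one of its examples. An Early Treatment Termination visit is mapped to the next scheduled nominal visit "if the Early Treatment Termination visit falls within the study day visit window defined for that nominal visit". All data go to the subject listings.

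For laboratory shifts, SAP 4.5.5 uses the "worst post-baseline measurement, defined as the value numerically farthest outside of the normal range across all post-baseline visits through the end of the study".

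Protocol Appendix A schedules the ECG at Screening, Day 1, Week 6, Week 10 and Early Treatment Termination. It schedules none at Week 3.

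**The concern.** The SAP takes a worst value across visits for laboratory shifts and for the investigator's ECG call, but not for the QTc limits in msec described in the next paragraph. Because those limits are tied to routine visits, the rule on unscheduled data removes any unscheduled ECG from the counts. Two things follow for the absolute limits:

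1. An outlier seen only on an unscheduled ECG has no by-treatment count.
2. The reader of the table cannot always tell whether exceedances at two visits come from the same subject.

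The sparse ECG schedule makes both somewhat more important. Change from baseline in ECGs is one of the primary safety endpoints. The QTc limits support that endpoint, although they are not named in it.

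**Working it through.** The plan states no QTc rate and no figure to reproduce, so the check is a reading of the text plus counting bounds.

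**Inputs.** About 30 subjects randomized 2:1 (SAP 3.1): 30 × 2/3 = 20 on EP262 and 30 × 1/3 = 10 on placebo. ECG days come from Protocol Appendix A. The exceedance counts below are assumptions, and every subject is taken to have an ECG at both visits.

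**Step 1: which post-baseline ECGs are routine.** Week 6 is Day 43 ± 3, so its window opens on Day 43 − 3 = Day 40. From Day 2 to Day 39 there are 39 − 2 + 1 = 38 days with no routine ECG. A QTc value in that stretch comes from an unscheduled ECG or an Early Treatment Termination ECG. Week 10 is about 4 weeks after the last dose. Week 6 is therefore the one fixed post-baseline ECG in the treatment period.

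**Step 2: an outlier seen only on an unscheduled ECG.** The absolute limits are counted at routine visits (SAP 4.5.6.2), and unscheduled data are barred from by-visit summaries (SAP 4.1.2). The contribution to every by-visit count is 0. In a worst post-baseline row the same subject would count as:

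- EP262: 1/20 = 5.0%
- placebo: 1/10 = 10.0%
- overall: 1/30 = 3.3%

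**Step 3: subject incidence from two visit rows.** With a subjects above a limit at Week 6 and b at Week 10, the number above it at either visit lies between max(a, b) and min(n, a + b).

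| Arm | Week 6, Week 10 | Subjects ever above | Incidence |
|---|---|---|---|
| EP262, n = 20 | 1, 0 | 1 | 5.0% |
| EP262, n = 20 | 1, 1 | 1 to 2 | 5.0% to 10.0% |
| EP262, n = 20 | 2, 1 | 2 to 3 | 10.0% to 15.0% |
| EP262, n = 20 | 2, 2 | 2 to 4 | 10.0% to 20.0% |
| Placebo, n = 10 | 1, 0 | 1 | 10.0% |
| Placebo, n = 10 | 1, 1 | 1 to 2 | 10.0% to 20.0% |

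If either visit count is zero, the scheduled-visit incidence is fixed and nothing is lost.

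**Step 4: comparison of arms.** Take 2/20 against 1/10 at both visits. Each row reads 10% against 10%. Incidence at either visit is 10% to 20% in each arm, so the difference runs from 10 − 20 = −10 to 20 − 10 = +10 percentage points. This is the mechanical extreme for assumed counts, not a forecast.

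**The case against.** The strongest case is that little is hidden. With about 30 subjects and two fixed post-baseline ECGs, incidence can be rebuilt from the listings. An abnormal call on an unscheduled ECG can enter the worst-value shift table. A clinically significant ECG result may be an AE (Protocol 11.1.1) and is then counted by arm as a TEAE. By-visit summaries also give "mean, SD, SE, median, first (Q1) and third (Q3) quartiles, minimum, and maximum values", so a scheduled extreme is visible. Separate Week 6 and Week 10 rows keep treatment and off-treatment values apart, and vital signs are likewise summarised by visit. The protocol text provides no routine repeat ECG, so the frequency of unscheduled ECGs is unknown. The table templates mentioned in SAP 1 are not in the documents and could already contain the row.

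Most of this stands and keeps the point minor. It does not close the gap: listings give no count by arm, the shift table and the AE route carry no msec limit, and the by-visit maximum also leaves out unscheduled values.

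A reader might infer three stronger things that the documents do not support:

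- **That an unscheduled outlier enters no threshold count at all.** The >30 and >60 categories are threshold counts too, and their basis is unstated. Exclusion is established only for the absolute limits.
- **That Early Treatment Termination ECGs are discarded.** An ECG is scheduled at that visit, and SAP 4.5 intends available data up to termination to be analysed. It refers back to SAP 4.1.2, which does not say where such an ECG appears if it maps to no visit or to Visit 3, which has no ECG. The placement is unstated; a loss is not shown.
- **That the primary safety analysis is compromised.** Change from baseline in ECG intervals is still summarised at each scheduled visit, and no test or decision rule rests on the QTc limits.

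**Conclusion.** The point holds for the absolute limits, at minor severity. On the SAP wording, an unscheduled QTc above 450, 480 or 500 msec enters no by-treatment count of those limits. Incidence across Week 6 and Week 10 cannot be read from the table when both counts are non-zero. At planned arm sizes, one subject whose only exceedance is omitted moves incidence by 5 points on EP262 or 10 on placebo. A subject who also exceeds the limit at a scheduled visit is already counted there.

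This rests on the SAP text without its table templates, and on assumed counts. No sample size, power or error-rate figure is affected.

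**What to change.** In SAP 4.5.6.2:

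- Keep the by-visit rows.
- Add a subject-incidence row by treatment for the worst post-baseline value, for QTcF and QTcB >450, >480 and >500 msec and for change >30 and >60. Use scheduled, unscheduled, Early Treatment Termination and follow-up records.
- Use as denominator the subjects with at least one post-baseline value and, for change, also a baseline value.
- Show an on-treatment version too. Fix its cut-off after the last dose before unblinding, long enough to keep Early Treatment Termination ECGs, which are ideally done within 2 days of that dose.
- State whether the >30 and >60 categories are by visit, any post-baseline, or both.

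Optionally, add a sentence to SAP 4.1.2 on where an Early Treatment Termination visit is shown when it maps to no nominal visit or to one without that assessment.

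The cost is SAP wording and a few table rows, with no new data. There are two downsides. Subjects with more ECGs have more chances to exceed a limit. The pooled row also mixes on- and off-treatment values, which is why the on-treatment version should accompany it.
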